8 DISCONTINUATION CRITERIA

8.1 Discontinuation from Study Treatment

Participants MUST discontinue investigational product (and non-investigational product at the discretion of the investigator) for any of the following reasons:

- Participant's request to stop study treatment. Participants who request to discontinue study treatment will remain in the study and must continue to be followed for protocol specified follow-up procedures. The only exception to this is when a participant specifically withdraws consent for any further contact with him/her or persons previously authorized by participant to provide this information
- Any clinical adverse event (AE), laboratory abnormality or intercurrent illness which, in the opinion of the investigator, indicates that continued participation in the study is not in the best interest of the participant. Adverse events should be graded and managed according to NCI CTCAE (version 4.0) guidelines.
- Termination of the study by Bristol-Myers Squibb (BMS)
- Loss of ability to freely provide consent through imprisonment or involuntarily incarceration for treatment of either a psychiatric or physical (eg, infectious disease) illness. (Note: Under specific circumstances, and only in countries where local regulations permit, a participant who has been imprisoned may be permitted to continue as a participant. Strict conditions apply and BMS approval is required.)

- Documented radiographic disease progression per RECIST v1.1.
 - Note: For 2L and 3L+ mCRC participants in Cohorts 4 and 6, treatment beyond progression is permitted. See [Section 8.1.5](#).
- Criteria listed in [Section 8.1.1](#) thru [8.1.4](#).
- Requiring treatment as listed in [Section 7.7](#).

Any criteria leading to the discontinuation of nivolumab, ipilimumab, or trametinib as part of the triplet investigative regimen in Parts 1B and 2 will require discontinuation of the entire regimen.

Discontinuation of the study treatment for abnormal liver tests should be considered by the investigator when a participant meets one of the conditions outlined in the protocol ([Section 8.1](#), [Appendix 5](#), and [Appendix 6](#)) or if the investigator believes that it is in best interest of the participant.

Refer to the Schedule of Activities for data to be collected at the time of treatment discontinuation and follow-up and for any further evaluations that can be completed.

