In the case of pregnancy, the investigator must immediately, within 24 hours of awareness of the pregnancy, notify the BMS Medical Monitor/designee of this event. In most cases, the study treatment will be permanently discontinued in an appropriate manner (eg, dose tapering if necessary for participant safety). Refer to [Section 9.2.5](#) Pregnancy.

All participants who discontinue study treatment should comply with protocol specified follow-up procedures as outlined in [Section 2](#). The only exception to this requirement is when a participant withdraws consent for all study procedures including post-treatment study follow-up or loses the ability to consent freely (ie, is imprisoned or involuntarily incarcerated for the treatment of either a psychiatric or physical illness).

If study treatment is discontinued prior to the participant's completion of the study, the reason for the discontinuation must be documented in the participant's medical records and entered on the appropriate case report form (CRF) page.

The assessment for discontinuation of nivolumab should be made separately from the assessment made for discontinuation of ipilimumab. Although there is overlap among the discontinuation criteria, if discontinuation criteria are met for ipilimumab but not for nivolumab, treatment with nivolumab may continue if ipilimumab is discontinued.

If a participant in any of the nivolumab/ipilimumab combination arms meets criteria for discontinuation and investigator is unable to determine whether the event is related to both or one study drug, the participant should discontinue both nivolumab and ipilimumab and be taken off the treatment phase of the study.

Participants are permitted to continue with nivolumab in combination with trametinib if deemed medically appropriate by the treating physician to manage toxicity, and in consultation with Medical Monitor/designee. Continuation with ipilimumab in combination with trametinib is not

permitted. For participants in Part 1A or Part 1, changes in study treatment are not permitted during the DLT observation period. See [Section 7.1.2](#) trametinib dosing for further detail.

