8.1.2 Nivolumab and Ipilimumab Dose Discontinuation

For participants who receive nivolumab in combination with ipilimumab and trametinib, study treatment should be permanently discontinued for the following:

- Any Grade 2 drug-related uveitis, eye pain or blurred vision that does not respond to topical therapy and does not improve to Grade 1 severity within the re-treatment period OR requires systemic treatment
- Any Grade 3 non-skin, drug-related adverse event lasting > 7 days, or recurs, with the following exceptions for laboratory abnormalities, diarrhea, colitis, neurologic toxicity, drug-related uveitis, pneumonitis, bronchospasm, hypersensitivity reactions, infusion reactions, and endocrinopathies:
 - Grade 3 drug-related diarrhea, colitis, neurologic toxicity, uveitis, pneumonitis, bronchospasm, myocarditis, hypersensitivity reaction, or infusion reaction of any duration requires discontinuation
 - Grade 3 drug-related endocrinopathies, adequately controlled with only physiologic hormone replacement do not require discontinuation. Adrenal insufficiency requires discontinuation regardless of control with hormone replacement.
 - Grade 3 drug-related laboratory abnormalities do not require treatment discontinuation except:
 - ◆ Grade 3 drug-related thrombocytopenia > 7 days or associated with bleeding requires discontinuation
 - ◆ Any drug-related liver function test (LFT) abnormality that meets the following criteria require discontinuation:
 - Grade \geq 3 drug-related AST, ALT or Total Bilirubin requires discontinuation*

- Concurrent AST or ALT $> 3 \times$ ULN and total bilirubin $> 2 \times$ ULN

* In most cases of Grade 3 AST or ALT elevation, study treatment(s) will be permanently discontinued. If the investigator determines a possible favorable benefit/risk ratio that warrants continuation of study treatment(s), a discussion between the investigator and the BMS Medical Monitor/designee must occur.

- Any Grade 4 drug-related adverse event or laboratory abnormality (including but not limited to creatinine, AST, ALT, or Total Bilirubin), except for the following events which do not require discontinuation:
 - Grade 4 neutropenia ≤ 7 days
 - Grade 4 lymphopenia or leukopenia or asymptomatic amylase or lipase
 - Isolated Grade 4 electrolyte imbalances/abnormalities that are not associated with clinical sequelae and are corrected with supplementation/appropriate management within 72 hours of their onset

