 - Grade 4 drug-related endocrinopathy adverse events, such as, hyper- or hypothyroidism, or glucose intolerance, which resolve or are adequately controlled with physiologic hormone replacement (corticosteroids, thyroid hormones) or glucose-controlling agents, respectively, may not require discontinuation after discussion with and approval from the BMS Medical Monitor/designee.
- Any event that leads to delay in dosing lasting > 10 weeks from the previous dose requires discontinuation, with the following exceptions:
 - Dosing delays to allow for prolonged steroid tapers to manage drug-related adverse events are allowed.
 - Dosing delays lasting > 10 weeks from the previous dose that occur for non-drug-related reasons may be allowed if approved by the BMS Medical Monitor/designee. Prior to re-initiating treatment in a participant with a dosing delay lasting > 10 weeks, the BMS Medical Monitor/or designee must be consulted. Tumor assessments should continue as per protocol even if dosing is delayed. Periodic study visits to assess safety and laboratory studies should also continue every 4 weeks or more frequently if clinically indicated during such dosing delays.
- Any adverse event, laboratory abnormality, or intercurrent illness which, in the judgment of the Investigator, presents a substantial clinical risk to the participant with continued nivolumab + ipilimumab dosing.

Any criteria leading to the discontinuation of nivolumab, ipilimumab, or trametinib as part of the triplet investigative regimen in Parts 1B and 2 will require discontinuation of the entire regimen.

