8.1.3 Trametinib Dose Discontinuation

A maximum of 2 trametinib dose level reductions are allowed for Part 1 and Part 1A. Only 1 dose level reduction is permitted for Parts 1B and 2. If a third dose level reduction is required for Part 1 or 1A, or dose reduction below 1.0 mg per day is required, study treatment should be permanently discontinued. In addition, discontinue trametinib permanently for the following:

- Any event that leads to delay in dosing for > 10 weeks from the previous dose requires discontinuation with the following exception:
 - Dosing delays > 10 weeks that occur for non-drug-related reasons may be allowed if approved by the BMS Medical Monitor. Prior to re-initiating treatment in a subject with a dosing delay lasting > 10 weeks, the BMS Medical Monitor must be consulted. Tumor assessments should continue as per protocol even if dosing is delayed.
- Any AE, laboratory abnormality, or intercurrent illness which, in the judgment of the investigator, presents a substantial clinical risk to the subject with continued treatment

Any criteria leading to the discontinuation of nivolumab, ipilimumab, or trametinib as part of the triplet investigative regimen in Parts 1B and 2 will require discontinuation of the entire regimen.

Refer to [Appendix 6](#) for additional dose discontinuation criteria.

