Section 8.1: Discontinuation from Study Treatment	Added the following text: “Any criteria leading to the discontinuation of nivolumab, ipilimumab, or trametinib as part of the triplet investigative regimen in Parts 1B and 2 will require discontinuation of the entire regimen.”	Added to clarify treatment discontinuation requirements.
Section 8.1.2: Nivolumab and Ipilimumab Dose Discontinuation		
Section 8.1.3: Trametinib Dose Discontinuation		
Section 9.4.3: Ophthalmic Examination	Added note for ophthalmic examination at screening that 7-day window does not apply at Cycle 1 Day 1.	Added to clarify timing of ophthalmic examination at screening.

Summary of Key Changes of Protocol Amendment 03		
Section Number & Title	Description of Change	Brief Rationale
Appendix 2: Study Governance Considerations	
The following modifications were made:
 
 Updated first paragraph of Monitoring section to further describe that details on monitoring can be found in the monitoring plan. Added section for Dissemination of Clinical Study Data. 	
These changes were made to:
 
 Clarify expectations for monitoring. Provide details on how clinical study information will be made available.
Appendix 4: Women of Childbearing Potential Definitions and Methods of Contraception	
Updated to include:
 
 An introductory paragraph Guidance for females treated with hormone replacement therapy Description of end of relevant systemic exposure Combined (estrogen- and progestogen-containing) hormonal contraception and progesterone-only hormonal contraception as highly effective methods that are user dependent Clarification that periodic sexual abstinence, withdrawal, spermicides only, and lactational amenorrhea method are not acceptable methods 	Updated to reflect the most recent BMS guidance.
Appendix 5: Nivolumab Management Algorithms for Studies Under CTCAE Version 4.0	Updated the appendix title to clarify that the management algorithms were specific to CTCAE version 4.0 and updated the guidance for each of the algorithms to the latest version.	Updated to reflect the most recent management algorithms for CTCAE version 4.0.
All	Minor formatting and typographical corrections.	These changes are minor and, therefore, have not been summarized.

Overall Rationale for the Revised Protocol 02, 06-Oct-2020

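### Section 8.1 contradicts itself for the Parts 1B and 2 triplet: one rule stops the whole regimen, while two sentences allow part of it to continue

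*Combined protocol and SAP*

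**What the plan says.** The stop-all rule is in Section 8.1. A criterion that ends any one of the three drugs "as part of the triplet investigative regimen in Parts 1B and 2 will require discontinuation of the entire regimen". Section 8.1.2 repeats it, opening with "Any criteria leading to the discontinuation of nivolumab, ipilimumab, or trametinib as part of the triplet investigative regimen in Parts 1B and 2", and so does Section 8.1.3 ("will require discontinuation of the entire regimen"). Section 7.1.4.1 has an equivalent sentence for Cohort 4. The Amendment 03 summary in Appendix 14 gives the reason for inserting the sentence in Sections 8.1, 8.1.2 and 8.1.3: "Added to clarify treatment discontinuation requirements".

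Later in Section 8.1, two sentences point the other way, and neither names a Part or cohort:

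- On nivolumab: "if discontinuation criteria are met for ipilimumab but not for nivolumab, treatment with nivolumab may continue if ipilimumab is discontinued".
- On the two-drug remainder: "Participants are permitted to continue with nivolumab in combination with trametinib if deemed medically appropriate by the treating physician to manage toxicity". This route also calls for consultation with the Medical Monitor or designee.

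The surrounding text does not conflict with the stop-all rule. Where the investigator cannot tell which drug caused the event, "the participant should discontinue both nivolumab and ipilimumab and be taken off the treatment phase of the study". Ipilimumab plus trametinib is barred. Parts 1 and 1A are named only to bar treatment changes during the dose-limiting toxicity (DLT) period.

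**The concern.** This is a rule for stopping toxic treatment in a three-drug regimen, and it gives two answers to one question: if only ipilimumab has to stop, may the participant stay on the rest? One site could stop all three drugs while another continues nivolumab, or nivolumab plus trametinib, each pointing to Section 8.1. The second site would be in breach of the mandatory sentence while following text printed in the same section.

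At stake are the uniformity of toxicity stopping in Cohorts 4 and 6, the classification of protocol deviations, and the meaning of the exposure and discontinuation data. A participant recorded as off ipilimumab could be off study treatment at one site and still dosed at another. Section 5.1.4 states that the study has no data monitoring committee.

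**Working it through.** No arithmetic decides this point, so the check sets the provisions side by side.

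**Test case.** A Cohort 4 or Cohort 6 participant is considered to meet a discontinuation criterion for ipilimumab only.

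| Provision | Ipilimumab | Nivolumab | Trametinib |
|---|---|---|---|
| Stop-all rule (8.1, 8.1.2, 8.1.3; 7.1.4.1 for Cohort 4) | stop | stop | stop |
| First permissive sentence (8.1) | stop | may continue | not mentioned |
| Second permissive sentence (8.1) | stop (implied) | may continue, with consultation | may continue, with consultation |

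The last two rows allow what the first forbids.

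**Does a scope limit separate them?** The stop-all rule names Parts 1B and 2. The permissive sentences name no Part, and the paragraph between them covers every arm that combines nivolumab and ipilimumab, which includes Cohorts 4 and 6.

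**Could the permissive sentences belong to another Part?**

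- Part 1A: Section 7.1.5 tells triplet participants to stop all study treatment if any one drug must stop permanently. The permissive sentences conflict with that too.
- Part 1: the doublet contains no ipilimumab, and Section 7.1.3 bars continuing on one component alone.

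**Does a ranking rule elsewhere resolve it?**

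- Section 3.3.2 prefers the stricter guideline when study and local guidelines differ.
- Sections 3.3 and 7.4 and Appendices 5 and 6 prefer the stricter toxicity guideline for events that may relate to the combination.
- These lean towards stopping everything, but none addresses two sentences within Section 8.1.
- The cross-reference to Section 7.1.2 in the permissive paragraph leads only to instructions for taking trametinib.

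**How usable is each permission?** Section 8.1.2 gives one joint list: "For participants who receive nivolumab in combination with ipilimumab and trametinib, study treatment should be permanently discontinued for the following". There are no ipilimumab-only criteria, so the first permission has little to act on beyond investigator attribution. The second is the more usable route, and consultation limits it.

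**Where is the gap widest?** Sections 7.1.4.1 (Cohort 4) and 7.1.5 (Part 1A) carry a stop-all sentence in the dosing text. Section 7.1.6 (Cohort 6) does not, so Part 1B sites depend on Section 8.1 and its subsections.

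**Size.** The planned triplet population in these Parts is about 80 (Cohort 4) + 80 (Cohort 6) = 160. That is the group to which the text could apply, not an estimate of how many it touched. The documents give no rate of ipilimumab-only discontinuation from which to estimate that number.

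**The case against.** The best defence is that the specific rule governs the general one. The stop-all sentence names Parts 1B and 2, is mandatory and appears three times, while the opposing sentences only permit. An investigator who stops everything complies with both, so it goes too far to say that the two texts cannot both be followed. That is correct, and it limits the fault to cases where a permission is used. It does not remove the fault, because nothing in Section 8.1 tells the investigator that the permission is unavailable in Cohorts 4 and 6.

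A second defence places the permissive sentences in Part 1A after the DLT period. Section 7.1.5 says participants should stop, which is weaker than the wording for Parts 1B and 2, so this reading is not excluded outright. It still runs against the plain sense of Section 7.1.5.

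A reader might also count as a third conflict the sentence requiring separate assessment of nivolumab and ipilimumab. It governs assessment, not continuation. An investigator can attribute an event to one drug, as Section 7.4 asks, and then stop all three. Two sentences conflict.

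A reader might infer that the permissive sentences are leftovers from an earlier protocol. The change history dates the insertion of the stop-all rule but not the opposing text, so this remains an inference.

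**Conclusion.** Wrong as written; severity minor. Section 8.1 both requires stopping the entire triplet and permits part of it to continue, for the same participants and with no order of precedence. Stop-all is almost certainly what the sponsor intends, given its repetition, its mandatory wording and the recorded reason for adding it. That conclusion about intent rests on reading the documents together, since no sentence states it.

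The number affected is unknown and may be zero. The consequence is for consistency of toxicity stopping and of the exposure and discontinuation data in Cohorts 4 and 6.

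Two larger conclusions may tempt a reader and are not supported:

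- **Bias in the primary endpoint.** Any effect on objective response rate is indirect. Section 9.1.1.2 continues imaging whether treatment is given, held or discontinued, and Section 10.3.1 ends the best-response window at progression or subsequent therapy.
- **Continued dosing with a drug whose own stopping criteria were met.** The first permission applies only when nivolumab's criteria are not met. The second requires medical appropriateness and consultation, and it does not waive any drug's criteria.

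How the analysis treats partial regimens is left to the separate statistical analysis plan mentioned in Section 10.3, so no fault in the analysis is claimed.

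**What to change.** Delete two sentences from Section 8.1: the one allowing nivolumab to continue after ipilimumab stops, and the one permitting nivolumab plus trametinib. Deletion is cleaner than marking them not applicable to Parts 1B and 2, because such a label would leave the conflict with Section 7.1.5 for Part 1A.

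Keep the unclear-attribution rule, the bar on ipilimumab plus trametinib and the DLT-period restriction for Parts 1 and 1A. The separate-assessment sentence may stay if it is limited to attributing the event. Optionally, repeat the stop-all sentence in Section 7.1.6, which lacks it.

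The cost is close to nil: a short text change plus the ethics-committee approval or notification that Appendix 2 requires for amendments and administrative letters. Data collection, sample size and analysis are untouched. Enrollment closed on 30-Nov-2022 (Section 6), so the change would act on the remaining dosing decisions and on how past ones are classified.

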8.1.1 Nivolumab Dose Discontinuation (Part 1 Only)

For participants who receive nivolumab without ipilimumab, nivolumab treatment should be permanently discontinued for the following:

- Any Grade 2 drug-related uveitis, eye pain or blurred vision that does not respond to topical therapy and does not improve to Grade 1 severity within the re-treatment period OR requires systemic treatment
- Any Grade 3 non-skin, drug-related AE lasting > 7 days, or recurs, with the following exceptions for laboratory abnormalities, drug-related uveitis, pneumonitis, bronchospasm, neurologic toxicity, hypersensitivity reactions, infusion reactions, and endocrinopathies:
 - Grade 3 drug-related uveitis, pneumonitis, bronchospasm, neurologic toxicity, myocarditis, hypersensitivity reaction, or infusion reaction of any duration requires discontinuation
 - Grade 3 drug-related endocrinopathies, adequately controlled with only physiologic hormone replacement do not require discontinuation. Adrenal insufficiency requires discontinuation regardless of control with hormone replacement.
 - Grade 3 drug-related laboratory abnormalities do not require treatment discontinuation except:
 - ◆ Grade 3 drug-related thrombocytopenia > 7 days or associated with bleeding requires discontinuation
 - ◆ Grade \geq 3 drug-related AST, ALT or Total Bilirubin requires discontinuation*
 - ◆ Concurrent AST or ALT $> 3 \times$ ULN and total bilirubin $> 2 \times$ ULN

* In most cases of Grade 3 AST or ALT elevation, study treatment (s) will be permanently discontinued. If the investigator determines a possible favorable benefit/risk ratio that warrants continuation of study treatment(s), a discussion between the investigator and the BMS Medical Monitor/designee must occur.

- Any Grade 4 drug-related adverse event or laboratory abnormality (including but not limited to creatinine, AST, ALT, or Total Bilirubin), except for the following events which do not require discontinuation:
 - Grade 4 neutropenia \leq 7 days
 - Grade 4 lymphopenia or leukopenia or asymptomatic amylase or lipase
 - Isolated Grade 4 electrolyte imbalances/abnormalities that are not associated with clinical sequelae and are corrected with supplementation/appropriate management within 72 hours of their onset
 - Grade 4 drug-related endocrinopathy adverse events, such as, hyper- or hypothyroidism, or glucose intolerance, which resolve or are adequately controlled with physiologic hormone replacement (corticosteroids, thyroid hormones) or glucose-controlling agents,

respectively, may not require discontinuation after discussion with and approval from the BMS Medical Monitor/designee.

- Any event that leads to delay in dosing lasting > 10 weeks from the previous dose requires discontinuation, with the following exceptions:
 - Dosing delays to allow for prolonged steroid tapers to manage drug-related adverse events are allowed.
 - Dosing delays lasting > 10 weeks from the previous dose that occur for non-drug-related reasons may be allowed if approved by the BMS Medical Monitor/designee.
 - Prior to re-initiating treatment in a participant with a dosing delay lasting >10 weeks, the BMS Medical Monitor (or/designee) must be consulted. Tumor assessments should continue as per protocol even if dosing is delayed. Periodic study visits to assess safety and laboratory studies should also continue every 4 weeks or more frequently if clinically indicated during such dosing delays.

Any adverse event, laboratory abnormality, or intercurrent illness which, in the judgment of the Investigator, presents a substantial clinical risk to the participant with continued nivolumab dosing.

